${\bf Appendix}\; {\bf 1-Protocol}\; {\bf and}\; {\bf Protocol}\; {\bf Amendments}$

Document	Version	Effective date	
Final Protocol	Version 0.2	27 May 2014	

No Protocol Amendments have been issued.

GlaxoSmithKline group of companies

TITLE PAGE

Division: Worldwide Development

Information Type: Worldwide Epidemiology Study Protocol

Title:	REVIEU - A multinational, retrospective, observational drug
	utilisation study of REVOLADE TM (eltrombopag) In selected
	countries in the European Union

Compound **Number:**

SB-497115-GR

Development Phase IV

27-MAY-2014 **Effective Date:**

Chronic Hepatitis C Virus, Immune Thrombocytopenia, Drug **Subject:**

Utilisation Study

Author(s):

Copyright 2014 the GlaxoSmithKline group of companies. All rights reserved.

Unauthorised copying or use of this information is prohibited

PASS information

Title	REVIEU- A multinational, retrospective, observational drug utilisation study of REVOLADE TM (eltrombopag) In selected countries in the European Union
Protocol version identifier	0.2
Date of last version of protocol	NA
EU PAS register number	Study to be registered after protocol is finalized
Active substance	Eltrombopag
Medicinal product	Eltrombopag
Product reference	SB-497115-GR
Procedure number	EMEA/H/C/001110/X/012G
Marketing	GlaxoSmithKline Trading Services Limited
authorisation	[name]
holder(s)	Ireland
	Telephone Number:
Joint PASS	No

and objectives	 The aim of this DUS is to provide real-world data on use and indications for use among REVOLADE users within several EU countries. The objectives of the study are: To document REVOLADE utilisation patterns according to the medical conditions and the patient age categories for which REVOLADE is being prescribed in selected European countries To characterize the patients who are prescribed REVOLADE in routine clinical practice.
Country(-ies) of study	Germany, Spain, France and other EU Member States as appropriate
Author	

MARKETING AUTHORISATION HOLDER(S)

Marketing authorisation holder(s)	GlaxoSmithKline Trading Services Limited				
noider(s)	[name]				
	Ireland Telephone Number				
	Telephone Number:				
	Telefax Number:				
MAH contact person					
	Email:				

TABLE OF CONTENTS

			PAGE
1.	LIST	OF ABBREVIATIONS	8
2.	RESF	PONSIBLE PARTIES	10
3.	ABST	FRACT	15
4.	AMEN	NDMENTS AND UPDATES	20
5.	MILES	STONES	20
6.	RATIO	ONALE AND BACKGROUND	21
	6.1.	Background	
	6.2.		

1. LIST OF ABBREVIATIONS

ADR Adverse drug reaction

AE Adverse event

ATC Anatomical Therapeutic Chemical

CI Confidence interval

CLL Chronic Lymphocytic Leukemia CRO Contract Research Organisation

DMP Data management plan
DUS Drug utilisation study
eCRF Electronic case report form
EDC Electronic data capture
EMA European Medicines Agency

ENABLE 1 Eltrombopag to INitiate and Maintain Interferon Antiviral

Treatment to Benefit Subjects with Hepatitis C related Liver

DiseasE

ENABLE 2 Eltrombopag to INitiate and Maintain Interferon Antiviral

Treatment to Benefit Subjects with Hepatitis C related Liver

DiseasE

ENCePP European Network of Centres for Pharmacoepidemiology and

Pharmacovigilance

EU European Union

EU PAS register European Union electronic register of post-authorisation studies

GPP Good Pharmacoepidemiology Practices
GVP Good Pharmacovigilance Practices

HCV Hepatitis C Virus HD Hodgkin's disease

ICF Informed consent form

ICMJE International Committee of Medical Journal Editors

IEC Independent ethics committee

ISPE International Society for Pharmacoepidemiology

ITP Immune Thrombocytopenia MA Marketing Authorisation

MAH Marketing Authorisation Holder

MedDRA Medical Dictionary for Regulatory Activities

mg Milligram Number

NHL non-Hodgkin's lymphomas

QA Quality assurance

SADR Serious adverse drug reaction

SAE Serious adverse event SAP Statistical analysis plan

SOP Standard operating procedure

STROBE STrengthening the Reporting of OBservational studies in

Epidemiology

WHO World Health Organisation

TRADEMARK INFORMATION

Trademarks of the GlaxoSmithKline group of companies

PROMACTATM / REVOLADETM

Trademarks not owned by the GlaxoSmithKline group of companies

Pegasys

Pegintron

SAS

3. ABSTRACT

Full Study Title:

REVIEU - A multinational, retrospective, observational drug utilisation study of **REVOLADE**TM (eltrombopag) in selected countries in the European Union (EU).

Rationale and Background:

Chronic primary immune thrombocytopenia (ITP) is an acquired immune mediated disorder characterized by isolated thrombocytopenia, defined as a peripheral blood platelet count less than 100×10^9 /L, lasting for more than 12 months, and the absence of any underlying cause (Rodeghiero, 2009).

In Europe, adult ITP has an incidence range of 1.6 to 3.9 cases per 100,000 personyears with increasing incidence with older age. Estimates of prevalence range widely from 9.5 to as high as 189.3 per 100,000 population; prevalence is similar amongst men and women, except in the mid-adult years (i.e., 30-60 years of age), when the disease is more prevalent in women (Deane, 2010).

In addition, in patients with chronic Hepatitis C virus (HCV), thrombocytopenia occurs most commonly in those with progressive liver disease and cirrhosis. In such patients, thrombocytopenia may render patients ineligible for antiviral treatment and require dose reductions or discontinuation and may also prevent patients from having liver biopsies and other invasive procedures, thereby hampering a physician's ability to stage and monitor the patient's liver condition. Until recently, the treatment options for thrombocytopenia in HCV affected patients were limited to intravenous immunoglobulins, corticosteroids, and cytokines, and in severe cases, splenectomy. It is estimated that the global prevalence of chronic HCV infection is 130–170 million with an annual incidence of 3–4 million (WHO, 2013).

REVOLADE (eltrombopag; GlaxoSmithKline, Research Triangle Park, NC, USA) is an oral, non-peptide, thrombopoietin receptor (TPO-R) agonist that interacts with the TPO-R and induces differentiation of hematopoietic stem and progenitor cells to megakaryocytes, and has been approved for the treatment of patients with chronic ITP and chronic HCV associated thrombocytopenia. It is intended that REVOLADE dosing requirements be individualised based on the patient's platelet count, with the objective of treatment not to normalize platelet counts but rather to maintain platelet counts above the level for hemorrhagic risk ($> 50 \times 10^9/L$).

The information generated by this study will be for the benefit of the European Medicines Agency (EMA), the Sponsor's stakeholders as well as to contribute to the published literature.

Research Question and Objectives:

REVOLADE received marketing authorization from the EMA in March 2010 for the treatment of adult splenectomised chronic ITP patients who are refractory to other treatments (e.g., corticosteroids, immunoglobulins). As part of the indication, REVOLADE may also be considered as second line treatment for adult non-splenectomised patients where surgery is contraindicated. REVOLADE was approved by the European Commission in September 2013 as a treatment for thrombocytopenia in adult patients with HCV, where the degree of thrombocytopenia is the main factor preventing the initiation or limiting the ability to maintain optimal interferon-based therapy.

It is generally acknowledged that prescribing practices of any particular drug in real life clinical practice may differ from its use as defined in the authorized indications. This drug utilisation study (DUS) for REVOLADE will be conducted in several European countries to determine the indications for use and patient age ranges for which REVOLADE is currently being prescribed. This DUS will also explore patient characteristics in order to better understand the patient population receiving REVOLADE in routine clinical practice.

The aim of this DUS is to determine indications for use among REVOLADE users within several EU countries utilizing real-world data obtained in medical charts.

The objectives of the study are:

- To document REVOLADE utilisation patterns according to the medical conditions and the patient age categories for which REVOLADE is being prescribed in selected European countries.
- To characterize the patients who are prescribed REVOLADE in routine clinical practice.

Study design:

This is a multi-national, multi-center study involving the retrospective review of approximately 300 to 450 patient medical records from selected European countries including France, Germany, Spain and possibly other countries, with each country having approximately six or seven sites. It is estimated that 18 to 21 hospital or office based sites overall, where prescribers of REVOLADE have been identified and medication records exist, will be targeted for recruitment. The investigators will be queried to identify REVOLADE-treated patients during the periods of interest. To meet the recruitment goal, additional EU country(ies) and sites may be added based on multiple factors including use of REVOLADE (compared to use approximated by sales data), available prescription data, market uptake, and favorable regulatory environment to conduct observational studies.

Medical records of all consecutive patients treated with REVOLADE, irrespective of indication, dose, treatment duration or any patient characteristic will be reviewed from first prescription of REVOLADE. This study is retrospective and therefore involves no intervention and will not impact the usual medical care nor affect the treatment of patients. The study will thus reflect real world medical practice without the potential for prescriber response bias which may occur in prospective studies (i.e., the Hawthorne Effect) (Mangione-Smith, 2002).

Study population:

Inclusion criteria

- Documented past treatment with REVOLADE (i.e., dispensed at least once by the pharmacy and patient received at least one dose) for whatever reason
- Patient (or a legal representative) has provided a written informed consent to participate in the study

Exclusion criteria

• Patients who participated or are participating in a randomized REVOLADE clinical trial

Variables

The following data will be collected for all patients enroled:

• Date of informed consent

The following data will be collected from *the medical records* for all patients enroled:

- Demographics [age at time of first REVOLADE prescribed dose, gender, race/ethnicity (where allowed by local regulation)]
- Primary diagnosis
- Medical history for applicable conditions and current medical conditions
- Treatment(s) preceding REVOLADE prescription (type, date, dose and duration)
- Concomitant treatment(s) with REVOLADE (type, date, dose and duration)
- All platelet counts ($x10^9/L$) at the time of primary medical condition, at initiation of REVOLADE, and dates, and resulting in dose change, by dose
- REVOLADE exposure (start date, stop date, doses)
- If REVOLADE discontinued, date and reason for discontinuation

Data Sources

This study is a retrospective medical chart review. Local site staff will review the medical chart of each enroled patient and extract the data.

These data will be entered pseudonymised into the eCRF via a secure web-based EDC system.

Study Size:

300 to 450 patients, enroled by approximately 18-21 sites will be recruited for participation in this study. It is planned to recruit all patients who are willing to participate, from all certified physicians in centers in selected EU countries, and without a minimum designated for any country, based on the estimated availability of eligible patients from the medical records within the planned recruitment period. Samples greater than 400 patients enable the estimation of the proportion of off-label use with an acceptable degree of precision. A sample size of 400 patients will allow the detection of a rate of 5% of off-label use with a precision of 2.1%, that is, the estimated proportion will be between 2.9% and 7.1%.

Data Analysis:

A Statistical Analysis Plan (SAP) describing the detailed statistical methodology and analysis will be provided as a separate document.

Continuous variables will be reported as mean, standard deviation, median and range. Categorical variables will be summarised as number and proportion of the total study population (counting missing data as a class), and by subgroups, where appropriate. Confidence intervals (as 95% CI) will be calculated using the method outlined by Newcombe (Newcombe, 1998) for the key variables.

All computations and generation of tables, listings and figures will be performed using SAS 9.1.3 or higher (SAS Institute, Cary, NC, USA) statistical software.

Estimated Milestones

- Final protocol submitted to the PRAC: October 2013
- Protocol approved with PRAC comments received: January 2014
- Sign Off of the updated protocol: May 2014
- Submission to the EU-PAS register: June 2014
- Start of data collection: September 2014
- End of data collection: 8 months after start of abstraction, April- May 2015
- Final study report: October 2015, i.e., 6 months after end of abstraction/study collection

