8.2.3. Study Duration

The eligibility period begins within the period immediately after REVOLADE has been launched in a given country (for instance, REVOLADE launch dates for the chronic ITP indication are in Germany, France and Spain, April 2010, January 2011, and December 2010, respectively) until the index date chosen as the start date of data abstraction i.e., September 2014 (Figure 1).

The observational period for each patient is the interval between the first dose of REVOLADE and the last dose if discontinued before September 2014. If a patient stops and re-starts REVOLADE during the observation period, all repeated treatment intervals will be captured. Also, if the patient is still on REVOLADE at the end of the study period, September 2014, then the observation period is between first dose and September 2014.

The planned duration of the study is approximately 14 months after the inclusion of the first patient. This period takes into account 8 months of data collection and study start-up and a 6 month period between last patient in and final study report.

GSK will closely monitor inclusion rates. If projected recruitment rates indicate that patient targets may not be achieved in the planned recruitment period, consideration will be given to extending the recruitment period, initiating additional sites within the three existing countries, and/or expanding the study into additional EU countries.

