8.2.5. Patient Enrolment

Since the purpose of this study is to evaluate routine clinical use of REVOLADE, patients will be identified based on the prescription of REVOLADE rather than on a specific diagnosis or condition.

The study population will consist of patients who have been prescribed REVOLADE for whatever reason according to the data retrieved in the medical records, provided they gave informed consent, had not or were not currently participating in a REVOLADE clinical trial, and used REVOLADE within the time period defined below. The medical records of all patients treated with REVOLADE in a participating centre will be reviewed for inclusion in this retrospective study, until the overall target number of at least 300 patients has been reached, irrespective of indication, medical condition, dose and treatment duration.

Patients are eligible for inclusion in study if their first prescription of REVOLADE was given between the period immediately after REVOLADE launch date and the start date for data abstraction i.e., September 2014. Patients who have been first prescribed REVOLADE after September 2014 will not be included in the study in order to ensure that study procedures do not influence prescribing practices. Informed consent will be

obtained as per country-specific regulations. Assuming the country-based first launched dates of REVOLADE in its initial chronic ITP indication (see Figure 1), the eligibility periods in the three selected countries thus span between January 2011 and September 2014 for France, April 2010 and September 2014 for Germany and December 2010 and September 2014 for Spain.

The earliest launch date for the chronic HCV-associated thrombocytopenia indication in these countries can be no sooner than September 2013, corresponding to the date it was approved by the European Commission. Considering that approval of HCV-associated thrombocytopenia indication was just recently, the number of expected HCV-associated thrombocytopenia patients therefore will be very small.

It is expected that approximately six or seven sites will be identified per country, and that up to 50 medical records will be abstracted at each site accounting for a total of 300 to 450 patients for the study.

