8.6.3. File Retention and Archiving

To enable audits from regulatory authorities or GSK, the investigator must agree to keep records, including the identity of all participating patients, all original signed informed consent forms (ICFs), patient screening logs, copies of all eCRFs (which will be provided by sponsor at study end), source documents and adequate documentation of relevant correspondence. The records should be retained by the investigator. The records must be available for review in the event the site is selected for monitoring, audits, or inspections and must be safely archived following the study conclusion, according to local regulations or as specified in the contract, whichever is longer. In the event that archiving of the file is no longer possible at the site, the site will be instructed to notify GSK.

8.7. **Data Analysis**

8.7.1. **DUS Analyses**

This is a multinational, retrospective, observational, medical chart review study. A Statistical Analysis Plan (SAP) describing the detailed statistical methodology and analysis will be provided as a separate document.

Continuous variables will be reported as mean, standard deviation, median and range. Categorical variables will be summarised as number and proportion of the total study population (counting missing data as a class), and by subgroups if and where appropriate. Confidence intervals (as 95% CI) will be calculated using the method outlined by Newcombe (Newcombe, 1998) for the key variables.

Participating physicians

Number of participating physician, and practice setting, will be summarized descriptively.

Page 126

Patient demographics and disease characteristics

Descriptive statistics will be given for the variables below:

- Age at time of initial REVOLADE prescribing dose
- Gender
- Race/Ethnicity
- Relevant medical history for applicable conditions

REVOLADE Patient characteristics

Number and percentage of the following categories will be described and stratified if number permits according to the dates of new indication approval:

- Adult chronic ITP patients
- Adult patients with HCV and clinically meaningful thrombocytopenia
- Patients < 18 years with chronic ITP
- Patients < 18 years with HCV (with and without thrombocytopenia)
- Patients < 18 years without chronic ITP or HCV but with another disease type, by specific disease type
- Adult patients with cancer, by cancer type
- Adult patients with myelodysplastic syndrome/AML

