- Adult patients receiving surgery during the observation period
- Adult patients in any other disease groups, by specific disease type

REVOLADE Utilisation characteristics

Descriptive statistics will be given for the variables below:

- Duration of REVOLADE treatment, stratified by the categories described above (if numbers permit)
- Initial dose (25 mg, 50 mg or other)
- Dose changes
- Rationale for dose changes
- Reason for temporary or permanent discontinuation

Platelet count characteristics

Descriptive statistics will be given for the variables below:

- Platelet count (x10⁹/L) at the time of primary medical condition, at initiation of REVOLADE, overall and by indication and by initial starting dose
- Platelet count resulting in dose change, by dose

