8.7.3. General Considerations

All computations and generation of tables, listings and figures will be performed using SAS 9.1.3 or higher (SAS Institute, Cary, NC, USA) statistical software.

The analysis methods will be fully described in a SAP written and finalised before database lock. Data will be presented for the whole study population and per country (as appropriate).

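### Crude shares discontinued and crude counts of dose changes depend partly on how long each patient could be observed; report them at fixed times from first dose.

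*Protocol*

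**What the plan says.** The Abstract (Data Analysis) and Section 8.7.1 give the same rule. Continuous variables get mean, standard deviation, median and range. For the rest, "Categorical variables will be summarised as number and proportion of the total study population", with missing data as a class of its own, and by subgroup where appropriate.

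Under the utilisation characteristics in Section 8.7.1, descriptive statistics are promised for treatment duration, initial dose, dose changes, the rationale for dose changes, and "Reason for temporary or permanent discontinuation". Of these, only duration is expressly split by patient category, if numbers allow. Section 8.7.3 adds presentation by country, as appropriate.

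Section 8.2.3 defines follow-up: "The observational period for each patient is the interval between the first dose of REVOLADE and the last dose if discontinued before September 2014". For a patient still on drug, it ends in September 2014. Section 8.2.5 gives the entry windows: "the eligibility periods in the three selected countries thus span between January 2011 and September 2014 for France, April 2010 and September 2014 for Germany", with Spain from December 2010. It also says that HCV use under the new indication cannot precede September 2013 and that HCV numbers are expected to be very small. One dose is enough for inclusion (Section 8.2.1).

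The protocol names no fixed time point, time-on-drug denominator or censoring method for dose changes or discontinuations.

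**The concern.** A discontinuation or a dose change can be recorded only while the patient is under observation. A patient started in April 2010 had 53 months in which to stop, and one started in August 2014 had about one. With all patients as denominator, both count equally as not discontinued if still on drug at the cut-off.

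The first objective (Section 7) is utilisation patterns classified by medical condition and age. Crude shares set against condition or country would mix prescribing behaviour with calendar time since launch. Later starters, including every on-label HCV patient, would tend to show fewer stops and fewer dose changes, and a larger proportion of the reasons recorded would be early ones. A reader of the final report could take this for better persistence or steadier dosing.

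**Working it through.** **Inputs from the protocol.** Launch dates (Sections 8.2.3 and 8.2.5): Germany April 2010, Spain December 2010, France January 2011. HCV approval: September 2013. Common cut-off: September 2014.

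**Maximum potential follow-up.**
- Germany: 4 years 5 months = 53 months
- Spain: 3 years 9 months = 45 months
- France: 3 years 8 months = 44 months
- On-label HCV: 12 months

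For a patient who stopped, observation ends at the last dose, so its length is partly the outcome itself. The relevant quantity is potential follow-up, from first dose to September 2014.

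**Assumptions.** The protocol gives neither event rates nor the distribution of start dates. I assume starts spread evenly over each window and the same constant hazard L of a first discontinuation in every group, with L = 0.3 per year and a range of 0.1 to 0.6.

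**Crude share discontinued by the cut-off**, for a window of T years: 1 − (1 − e^(−LT)) / (LT).

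At L = 0.3:
- 53 months: LT = 1.325, e^(−LT) = 0.266; 1 − 0.734/1.325 = 0.446
- 44 months: LT = 1.100, e^(−LT) = 0.333; 1 − 0.667/1.100 = 0.393
- 12 months: LT = 0.300, e^(−LT) = 0.741; 1 − 0.259/0.300 = 0.136

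| Hazard per year | 53 months (Germany) | 45 months (Spain) | 44 months (France) | 12 months (on-label HCV) |
|---|---|---|---|---|
| 0.1 | 19% | 17% | 16% | 5% |
| 0.3 | 45% | 40% | 39% | 14% |
| 0.6 | 65% | 60% | 60% | 25% |

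The true hazard is equal along each row. The Germany–France gap is 3 to 5 points; the gap between the 53- and 12-month windows is 14 to 40 points.

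**By start date**, at L = 0.3, using 1 − e^(−Lt): a patient who started 53 months before the cut-off has a 73% chance of having stopped by then, and one who started 12 months before has 26%.

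**Dose changes at a constant rate.** Mean time on drug is the share discontinued divided by L. At L = 0.3 and one change per patient-year, expected changes per patient are 1.49 (53 months), 1.31 (44) and 0.45 (12).

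**Dose changes clustered early.** Section 6.1 describes adjustment after two to three weeks in ITP and every 2 weeks in HCV before antiviral therapy. As an illustration, assume 4 changes per year for the first 3 months, 0.2 per year afterwards, and L = 0.3.
- 53-month window: mean time on drug is 0.234 years in the first 3 months and 1.252 later. Changes = 4 × 0.234 + 0.2 × 1.252 = 1.19. Rate = 1.19/1.486 = 0.80 per patient-year.
- 12-month window: 0.211 and 0.242 years. Changes = 4 × 0.211 + 0.2 × 0.242 = 0.89. Rate = 0.89/0.454 = 1.97 per patient-year.

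The crude means now differ only 1.3-fold (1.19/0.89), while the overall rate differs 2.5-fold in the opposite direction (1.97/0.80), again with identical prescribing.

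**Fixed time point.** Under the same model, cumulative incidence of discontinuation at 6 months is 1 − e^(−0.15) = 14% in every group, whatever its window.

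**The case against.** The strongest reply is that the protocol defers detailed methodology to a SAP, promises only descriptive statistics for these variables, and collects every date needed. Reasons for stopping could be described among those who stopped, and dose changes as a number per patient. All of that is possible. But the protocol does more than stay silent: it states the form and the denominator twice, and a SAP that followed the stated rule would report crude shares.

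A reader might go further and infer that differences between indications, countries and start years will mostly reflect time observed. The documents do not support that:
- They give no event rates or start dates, so the artefact cannot be set against real differences.
- Between countries it is small. At 0.3 per year, Germany and France differ by about 5 points. If 300 to 450 patients split evenly over three countries (an assumption), there are 100 to 150 in each, and the 95% margin on the difference, 1.96 × √[(0.45 × 0.55 + 0.39 × 0.61)/n], is about ±14 to ±11 points.
- The 12-month window binds only on-label HCV use, which Section 8.2.5 expects to be very rare.
- No analysis of these events by start year is stated. The split by approval date, "stratified if number permits according to the dates of new indication approval", applies to the patient categories.

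The objection that an overall rate per patient-year is not a safe replacement also stands, as the early-titration illustration shows.

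**Conclusion.** The point holds in limited form. Follow-up is unequal by design and cut off administratively, and the stated summary does not allow for this in events that accumulate over time. Crude shares discontinued and crude dose-change counts therefore depend partly on time observed. Under the assumptions shown, the effect can be large by indication or start date and is modest between countries. For dose changes, its size depends heavily on how early they occur: the ratio between the 53- and 12-month windows is 3.3 at a constant rate but 1.3 with early titration.

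The study's main aim, indications for use, and the off-label share that drives the sample size do not depend on dose changes or discontinuations accrued during follow-up and are unaffected. This is a worthwhile, inexpensive improvement to the utilisation tables and no threat to the study.

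**What to change.** In Section 8.7.1 and the Abstract:
- Report discontinuation, overall and by reason, as cumulative incidence at fixed times such as 6 and 12 months from first dose. Censor patients still on drug at the September 2014 cut-off, and treat other reasons as competing events.
- Report dose changes within the same fixed windows, among patients who started at least that long before the cut-off.
- Keep the crude counts and shares as supporting output, with time on drug shown beside them.
- Do not make an overall rate per patient-year the lead measure, since it too varies with length of follow-up when dose changes cluster early.

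No new data are needed: Section 8.3.3 already collects start and stop dates, all changes in dose, and the date and reason for discontinuation. The cost is some wording and a few extra tables. The drawback is that the dose-change windows leave out the latest starters, possibly including some of the few HCV patients.
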